#### **4.2. Additional exclusions from MITT analysis**

1. Patients who, having completed treatment, are lost to follow-up or withdrawn from the study, their last status being culture negative and their last positive culture result (“isolated positive culture”) followed by at least two negative culture results at different visits (at least 7 days apart, without an intervening positive culture)
2. Women who become pregnant during treatment and stop their allocated treatment
3. Patients who died during treatment from violent or accidental cause (e.g. road traffic accident). N.B.: This does not include death from suicide, which will be considered an unfavourable outcome.
4. Patients who died during follow-up (after the end of treatment) with no evidence of failure or relapse of their TB, their last status being culture negative and their last positive culture result (“isolated positive culture”) followed by at least two negative culture results at different visits (at least 7 days apart), and who have not already been classified as unfavourable.
5. Patients who, after being classified as having culture negative status, are re-infected with a new strain from that with which they were originally infected. Reinfection will be defined specifically as a patient infected with a strain that is genetically different from the initial strain (see Mycobacteriology Laboratory Manual).
6. Patients who are able to produce sputum at 12 months, but whose 12-month visit sputum samples are all contaminated or missing, who cannot be brought back for repeat cultures, provided they have not already been classified as unfavourable and provided their last positive culture was followed by at least two negative cultures. N.B.: This does not apply to patients who are unable to produce sputum at 12 months, or to patients who are able to be brought back subsequently and produce negative cultures.

Patients in categories 1-5 above who had already been classified as having an unfavourable outcome will not be excluded.

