#### **4.4. Lost to Follow-up or Early Withdrawal**

Lost to Follow-up or Early Withdrawals *before* the end of the treatment (month 4 or 6) are considered as unfavourable outcomes for ITT and MITT. However these patients will be excluded from the Per Protocol analysis. The MITT and Per Protocol analyses will consider Lost to Follow-up *after* end of treatment (month 4 and 6) as unassessable unless at the time of default from follow-up the patient a) was already classified as having an unfavourable outcome, b) did not have culture negative status, or c) had a positive culture result (“isolated positive culture”) not followed by at least two negative culture results at different visits (at least 7 days apart), in which cases the patient will be classified as having an unfavourable outcome. We believe this is the most appropriate approach for the primary analysis because together with the non-tuberculosis deaths, this group is likely to considerably out-number the bacteriological failures and relapses. These patients will be considered as having an unfavourable outcome in the ITT analysis.

There is a clear precedent for this analytic approach in other TB trials, and these trials also provide examples of why the inclusion of the losses to follow-up as unfavourable greatly affects the results.

Data from the Priftin trial which led to accelerated approval of rifapentine and a trial conducted by the International Union Against TB & Lung Disease (IUATLD) in African and Asian sites illustrate the problems associated with classifying all losses to follow-up and deaths as having an unfavourable outcome.

In the Priftin trial bacteriological relapses occurred in 5% of patients on the rifampicin based regimen compared to 11% on the rifapentine based regimen. Approximately one third of patients were lost to follow-up and when this group combined with patients unassessable for other reasons were added to the bacteriological failures, the rates increased to 53% and 57% respectively. The true bacteriological relapses were greatly outnumbered by these other groups. At the time of the licensing submission to the FDA it was recognised that because there were a substantial number of patients likely to be unassessable the main focus should be on the relapse rates. In the final statistical report the results were first reported excluding those unassessable and then assuming all losses had an unfavourable outcome and finally assuming all losses had a favourable outcome.

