#### **4.5. Definition of adequate treatment**

The definition of adequate treatment sets a limit for the amount of treatment missed. Patients not taking the adequate amount of treatment by this definition will be excluded from the PP analysis.

For patients allocated to a 6 month regimen, to meet the definition of adequate treatment they must have taken at least 146 doses (80%) of their allocated 182 day (26 weeks) treatment regimen within 203 days of starting therapy (i.e. 26 weeks plus an allowable 3 weeks extension ).

For patients allocated to a 4 month regimen, to meet the definition of adequate treatment they must have taken at least 96 doses (80%) of their allocated 119 day (17 weeks) treatment regimen within 140 days of starting therapy (i.e. 17 weeks plus an allowable 3 weeks extension ).

Patients in the control arm are additionally required to have taken at least 80% of their allocated intensive treatment.

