### **6.1.3. Unfavourable status in MITT population**

1. Patients not classified as having achieved or maintained culture negative status when last seen, or
2. Patients previously classified as having culture negative status who, following the end of treatment, have two positive cultures without an intervening negative culture, (however, see Section 3.3 for an exception), or
3. Patients who had a positive culture not followed by at least two negative cultures when last seen, or
4. Patients dying from any cause during treatment, except from violent or accidental cause (e.g. road traffic accident), not including suicide (eg, suicide will be considered an unfavourable outcome) or
5. Patients definitely or possibly dying from TB related cause during the follow-up phase or
6. Patients requiring an extension of their treatment beyond that permitted by the protocol, a restart or a change of treatment for any reason except reinfection or pregnancy, or
7. Patients failing to complete an adequate course of treatment, as defined in section 4.5, who were unassessable at 12 months, or
8. Patients lost to follow up or withdrawn from the study before the end of treatment

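### SAP 6.1.3(7) counts inadequately treated, unassessable patients as MITT failures, while 4.4, 4.2(1) and 4.2(6) can leave the same patients out; it also brings a control-only dosing test into MITT

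*SAP*

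**What the plan says.** Section 7 makes PP and MITT primary, and section 6 sorts each patient into one of three statuses: favourable, unfavourable or unassessable. The rules that meet on this point are:

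- **6.1.3(7)** lists as unfavourable in MITT "Patients failing to complete an adequate course of treatment, as defined in section 4.5, who were unassessable at 12 months". It has no exceptions.
- **4.4** treats MITT and PP patients lost after month 4 or 6 "as unassessable unless at the time of default from follow-up the patient a) was already classified as having an unfavourable outcome", or was not culture negative, or had a positive culture not yet followed by two negatives. Inadequate treatment is not among these exceptions.
- **4.2(1)** excludes from MITT "Patients who, having completed treatment, are lost to follow-up or withdrawn from the study, their last status being culture negative". It does not say whether completing treatment means meeting 4.5.
- **4.2(6)** excludes patients able to produce sputum "whose 12-month visit sputum samples are all contaminated or missing, who cannot be brought back for repeat cultures", provided they are not already unfavourable and their last positive was followed by two negatives. It sets no condition on treatment received.
- **4.5** requires 146 of 182 doses within 203 days, or 96 of 119 doses within 140 days, and adds: "Patients in the control arm are additionally required to have taken at least 80% of their allocated intensive treatment". Its stated purpose is exclusion from PP.

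**The concern.** Section 3.1 defines the treatment period by calendar time from the start of therapy. A patient can therefore pass month 4 or 6 culture negative with fewer than 80% of doses taken, and then be lost. Under 4.4 that patient is unassessable; under 6.1.3(7) the patient is a failure. A similar patient who attends at 12 months but yields only contaminated samples is excluded by 4.2(6) and a failure under 6.1.3(7). Two analysts who both follow the SAP could produce different MITT numerators and denominators.

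The reference to 4.5 adds a second problem. A control patient who passes the total-dose test but misses too much of the intensive phase, and is then unassessable, can become an MITT failure. A patient in the 6-month experimental arm with the same missed doses cannot. The non-inferiority verdict on each comparison decides whether the next is tested, so the classification should not be left to choice in an open-label trial.

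**Working it through.** **Setting the rules side by side**

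1. *Loss after end of treatment, under 80% of doses, culture negative.* Section 4.4 gives unassessable; 6.1.3(7) gives unfavourable. Under section 6 a patient cannot be both.
2. *All 12-month samples contaminated or missing, under 80% of doses.* Section 4.2(6) gives excluded; 6.1.3(7) gives unfavourable.
3. *Does the existing tie-break help?* Section 4.2 retains only patients previously classed as unfavourable. Item 7 cannot apply until the patient is found unassessable at 12 months, which is the same point at which 4.2(6) applies. The tie-break does not order them.
4. *If 4.2 and 4.4 always go first, with completion read by calendar,* item 7 has almost nothing left. Losses before end of treatment fall under item 8, patients not culture negative under item 1, and unresolved positives under item 3.
5. *Control-only test.* The total-dose rule tolerates 182 − 146 = 36 missed doses in a 6-month arm and 119 − 96 = 23 in a 4-month arm. A control patient within the 36 can still fail 4.5 if enough of the missed doses fall in the intensive phase. A patient in the 6-month experimental arm with the same missed doses passes, as does a 4-month patient with up to 23 missed.

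**Size**

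The SAP's sample size reproduces. With 16% in both arms, a 12-point margin, one-sided 2.5% and 90% power:

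n = 2 × 0.16 × 0.84 × (1.960 + 1.282)² / 0.12² = 196.1; 196.1 / (1 − 0.15 − 0.08) = 254.7, so 255 per arm, as Appendix 1 states.

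The same fraction applied to the 300 recruited gives 300 × 0.77 = 231 per arm, and 16% of 231 is 37. The SAP does not say how many patients fall in the overlap, so the counts below are assumptions. The bound is the unstratified Wald one, d + 1.96 × √[p₁(1 − p₁)/n₁ + p₀(1 − p₀)/n₀]; the SAP's own analysis is stratified.

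Moving k patients in one arm from excluded to unfavourable changes its rate by (37 + k)/(231 + k) − 37/231. For k = 3, 5 and 7 this is 1.1, 1.8 and 2.5 points. For scale, 48 against 37 of 231 is a difference of 4.8 points with an upper bound of 11.8%, which passes.

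Starting from 46 against 37 of 231:

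| Overlap counted unfavourable (intervention / control) | Intervention | Control | Difference (points) | Upper bound |
|---|---|---|---|---|
| none | 46/231 | 37/231 | 3.9 | 10.9% |
| 5 / 5 | 51/236 | 42/236 | 3.8 | 11.0% |
| 5 / 0 | 51/236 | 37/231 | 5.6 | 12.7% |
| 0 / 5 | 46/231 | 42/236 | 2.1 | 9.2% |
| 10 / 5 | 56/241 | 42/236 | 5.4 | 12.7% |
| 5 / 10 | 51/236 | 47/241 | 2.1 | 9.4% |

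Starting from equal rates (37/231 in both arms, bound 6.7%), five in the intervention arm only gives 8.6%, five in control only gives 5.0%, and 5 / 5 gives 6.9%. With ten in one arm only, the range is 3.4% to 10.4%, and the verdict does not change.

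**The case against.** The best defence is that the order is implied. Section 4 defines MITT by its exclusions, and 6.1.3 classifies whoever remains. Further, 4.2(1) and item 7 can be read as complements: patients who completed treatment are excluded on loss, and those who did not complete adequately are failures. On that reading 4.4 only assigns the unassessable label, on which item 7 then acts.

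Part of this stands. A reader might infer that item 7 also collides with the exclusions for pregnancy ("Women who become pregnant during treatment and stop their allocated treatment"), for accidental death ("Patients who died during treatment from violent or accidental cause") and for non-TB death in follow-up. The SAP does not support that. Those exclusions help define the population, the event comes before item 7 can apply, and 6.1.3 itself carves out accidental death in item 4 and pregnancy in item 6. These are not a material conflict.

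The complementary reading of 4.2(1) is sensible and gives item 7 content, but the SAP never links 4.2(1) to 4.5. It also leaves 4.4 in tension, since 4.4 sets unassessable against unfavourable and names the only routes from one to the other. It does nothing for 4.2(6).

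Section 8 gives partial cover: ITT is analysed with missing outcomes as unfavourable and as favourable, and MITT and PP with all deaths as unfavourable. PP, also primary, excludes inadequately treated patients not already unfavourable. None of these varies item 7 within MITT.

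The control-only effect is narrow. It needs a patient who fails the intensive-phase test, passes the total-dose test and is then unassessable.

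**Conclusion.** The contradiction is real in two places: 6.1.3(7) against 4.4, with 4.2(1) undefined, and 6.1.3(7) against 4.2(6). The control-only test carried in from 4.5 is a separate asymmetry, and its direction is known: it can only add control failures.

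A reader might go further and infer that the trial's conclusion turns on which rule is read first, or that the overlap as a whole favours the experimental regimens. Neither is supported. The SAP gives no count, the overlap can fall in either arm, and only the intensive-phase part has a fixed direction. Under the assumed counts, a net imbalance of about five moves the bound by 1.7 to 1.9 points and changes the verdict only when the result is already near 12%. A balanced 5 / 5 overlap moves it by about 0.1 point near the margin and 0.2 at equal rates. The effect is modest, but it falls on a primary classification and is cheap to remove.

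**What to change.** Amend the SAP before data by arm are seen:

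- State that exclusions 4.2(2) to 4.2(5) apply before 6.1.3(7).
- Define completion of treatment in 4.2(1) as meeting the total-dose part of 4.5.
- Add inadequate treatment as exception (d) in 4.4, and make adequate treatment a condition of exclusion under 4.2(6). The alternative to these alignments is to delete 6.1.3(7).
- For 6.1.3(7), use only the total-dose part of 4.5 in every arm; the intensive-phase test can stay for PP.
- Add to section 8 an MITT sensitivity analysis under the other classification.

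The cost is a few sentences and one extra analysis. A few more patients may count as unfavourable in MITT.

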### **6.1.4. Unfavourable status in PP population**

1. Patients not classified as having achieved or maintained culture negative status when last seen, or
2. Patients previously classified as having culture negative status who, following the end of treatment, have two positive cultures without an intervening negative culture, (however, see Section 3.3 for an exception), or
3. Patients who had a positive culture not followed by at least two negative cultures when last seen, or
4. Patients dying from any cause during the 6 month treatment phase, except from violent or accidental cause (e.g. road traffic accident), not including suicide (e.g., suicide will be considered an unfavourable outcome), or
5. Patients definitely or possibly dying from TB related cause during the follow-up phase, or
6. Patients requiring a restart or a change of treatment because of an unfavourable outcome with or without bacteriological confirmation, i.e. on bacteriological, radiographic or clinical grounds

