### 3. Definitions and data handling issues

#### 3.1. Definitions

**Positive culture** refers to the culture being positive for M.tb. N.B.: In the absence of the speciation data, the unconfirmed result will be treated as positive for M.tb. False positive or contaminated will be treated as missing. Specimens classified as non-tuberculous mycobacteria (NTM) and negative for M.tb will be treated as contaminated (adequate conditions for growth of M.tb exist if NTM grow). The bacteriology algorithm for reporting MGIT results can be found in STAND Laboratory Manual. Two sputum samples per visit are collected at each visit throughout treatment and follow-up. The culture result for a given visit is established using all samples obtained for that visit. A positive culture takes precedence over a negative culture at the same visit.

**Culture negative status** is achieved when a patient produces at least 2 negative culture results at different visits (at least 7 days apart) without an intervening positive culture result for M.tb. The date of the first negative culture of these two is the date at which culture negative status was obtained. Once obtained, culture negative status continues until there are two positive cultures at different visits (at least 7 days apart), without an intervening negative culture, or until there is a single positive culture not followed by two negative cultures. Culture negative status can be achieved at any time during treatment or follow-up but before any re-treatment and can be re-established.

Patients with two contaminated or missing samples at a given visit (from Month 2 onwards) will be asked to return to produce two more sputum samples. A single culture result or inability to produce sputum (see section 3.2) at 12 months will be sufficient to count that patient as having data for primary endpoint classification.

**Treatment failure or Bacteriologic failure** is defined as being declared an unfavourable status (as defined in section 6) at or before the end of treatment (either 4 or 6 months) or failing to attain culture negative status and being declared an unfavourable outcome.

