**Relapse or Bacteriologic relapse** is defined as failing to maintain culture negative status or being declared an unfavourable outcome after the end of treatment (either 4 or 6 months) in those patients who attained culture negative status by the end of treatment, and were re-infected with the **same** (as per the STAND Laboratory Manual) *Mycobacterium tuberculosis (MTB)* strain.

**Reinfection or Bacteriologic Reinfection** is defined as failing to maintain culture negative status or being declared an unfavourable outcome after the end of treatment (either 4 or 6 months) in those patients who attained culture negative status by the end of treatment and were infected with a *Mycobacterium tuberculosis (MTB)* strain that is **different** (as per the STAND Laboratory Manual) from the infecting strain at baseline.

**Clinical failure** is defined as a change from protocol-specified TB treatment or retreatment for TB during follow up as determined by the treating physician, or TB-related death.

The **treatment period** is defined as either 4 or 6 months from start of therapy depending on allocated treatment regimen and the **follow-up period** is defined as the period after the end of treatment to the end of follow-up.

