#### **4.3. Additional exclusions from PP analysis**

1. Patients lost to follow-up or withdrawn before the end of treatment, unless they have already been classified as having an unfavourable outcome.

2. Patients whose treatment was modified or extended for reasons (e.g. an adverse drug reaction or pregnancy) other than an unfavourable therapeutic response to treatment, unless they have already been classified as having an unfavourable outcome.

3. Patients not meeting the definition of having received an adequate amount of their allocated study regimen (see section 4.5 for definition), provided they have not already been classified as having an unfavourable outcome.

4. Patients who are classified as “major protocol deviations” (see below), unless they have already been classified as having an unfavourable outcome on the basis of data obtained prior to the protocol deviation.

A list of all protocol deviations will be compiled throughout the course of the study.

A **Major Protocol Deviation** is defined as a serious protocol deviation which is likely to affect to a significant degree the safety or physical or mental integrity of the subjects of the trial or the scientific value of the trial. These patients will be included in the ITT and MITT analyses, but not in the Per Protocol analysis. A list of all major protocol deviations will be approved by the study Coordinating Investigator before database lock.

A **Minor Protocol Deviation** is defined as a technical deviation which does not result in harm to the trial subjects or significantly affect the scientific value of the reported results of the trial.

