### **6.1.1. Favourable status (all analyses)**

Patients with a negative culture status at 12 months from start of therapy (from 50 weeks to 54 weeks), who had not already been classified as having an unfavourable outcome, and whose last positive culture result ("isolated positive culture") was followed by at least two negative culture results.

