## **7. Determination of statistical non-inferiority**

The first comparison to be tested will be the MPa200Z 6 month experimental regimen against the standard regimen. The second comparison to be tested will be the MPa200Z 4 month experimental regimen against the standard regimen. The third comparison to be tested will be the MPa100Z 4 month experimental regimen against the standard regimen. To preserve the type I error rate, the second comparison will only be tested if non-inferiority is demonstrated with the 6 month experimental regimen. Similarly the third hypothesis will only be tested if non-inferiority of the PA-824 200mg 4 month regimen has been demonstrated. This strategy means no adjustments are required for multiple comparisons.

Non-inferiority will be assessed using the upper bound of the two-sided 95% confidence interval for the difference between the proportion of participants who are classified as having an unfavourable status on the intervention and the control regimen.

If the upper bound of the two-sided 95% confidence limit for the difference, proportion with unfavourable status on intervention arm less the proportion with unfavourable outcome on the control arm, is less than 12% (the margin of non-inferiority) the intervention will be considered to be non-inferior to the control arm on that comparison.

The PP and MITT analyses will be considered primary. However, in order to declare an intervention to be non-inferior, consistent results should be obtained from the ITT analysis and from sensitivity and subgroup analyses, although not all of these will necessarily satisfy the strict definition of non-inferiority.

All primary efficacy analyses of the three main analysis populations will be adjusted for HIV status and cavitation, using a stratified analysis of the risk difference from each stratum using Cochran-Mantel-Haenszel weights.

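### The PP rules keep patients whose treatment was extended for poor response but, unlike the MITT rules, do not list that extension as unfavourable; SAP sections 4.3(2), 6.1.3(6) and 6.1.4(6) need to be reconciled

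*SAP*

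**What the plan says.** Four rules of the SAP bear on a patient whose treatment is prolonged beyond what the protocol permits.

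- **Who leaves PP.** Section 4.3(2) excludes "Patients whose treatment was modified or extended for reasons (e.g. an adverse drug reaction or pregnancy) other than an unfavourable therapeutic response to treatment". Anyone already classified as unfavourable is spared this exclusion. A patient extended because of poor response is outside it and remains in PP.
- **What counts as unfavourable in MITT.** Section 6.1.3(6) lists "Patients requiring an extension of their treatment beyond that permitted by the protocol, a restart or a change of treatment for any reason", with exceptions for reinfection and pregnancy.
- **What counts as unfavourable in PP.** Section 6.1.4(6) lists "Patients requiring a restart or a change of treatment because of an unfavourable outcome with or without bacteriological confirmation". Extension is not named.
- **What counts as favourable in every analysis.** Section 6.1.1 takes "Patients with a negative culture status at 12 months from start of therapy (from 50 weeks to 54 weeks"), provided that they are not already unfavourable and that any last positive culture was followed by at least two negatives. It sets no condition on extended treatment.

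Section 7 gives both populations primary standing: "The PP and MITT analyses will be considered primary".

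**The concern.** The carve-out in section 4.3(2) makes sense only if patients extended for poor response are kept so that they can be counted as failures. Section 6.1.4 contains no item that clearly does so. A patient who responds poorly, receives treatment beyond the permitted limit and is culture negative at 12 months would then be a PP success for the allocated regimen, although the outcome followed more treatment than that regimen provides.

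At stake are the PP result, which is one of two primary results in a gated non-inferiority sequence, and the agreement between PP and MITT. The same patient can carry opposite outcomes in the two analyses for no stated reason. In a non-inferiority comparison, failures missed in the experimental arm move the result towards the claim.

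**Working it through.** **1. Can another PP rule catch the patient?** Take a patient extended beyond the protocol for poor response who is culture negative at 12 months, with any last positive followed by two negatives.

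| SAP rule | Does it apply? |
|---|---|
| 4.3(2), exclusion for extension | No. It covers other reasons only. |
| 4.3(3) with 4.5, inadequate treatment | Not because of the extension. The rule is a minimum by a deadline: for a 6-month regimen, "they must have taken at least 146 doses (80%) of their allocated 182 day (26 weeks) treatment regimen within 203 days"; for a 4-month regimen, 96 doses within 140 days. Later doses do not disqualify. |
| 6.1.4(1) and (3), culture status when last seen | No, once the patient has converted. Section 3.1 allows late conversion: "Culture negative status can be achieved at any time during treatment or follow-up but before any re-treatment and can be re-established". |
| 6.1.4(2), two positives after the end of treatment | No, if cultures stay negative. |
| 6.1.4(4) and (5), deaths | No. |
| 6.1.4(6), restart or change | Only if a change is taken to include an extension. |
| 6.1.1, favourable | Yes, on a literal reading. |

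The last step but one turns on the word change. Section 6.1.3(6) sets extension, restart and change side by side as three events, and section 4.3(2) separates modified from extended treatment. A reader applying section 6.1.4(6) therefore cannot safely assume that extension is included.

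**2. The plan's own sample size.** Appendix 1 gives a 16% unfavourable rate, a 12% margin, 90% power, one-sided 2.5% significance, and losses of 15% plus 8%.

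n = 2 × 0.16 × 0.84 × (1.960 + 1.282)² / 0.12² = 196.1, so 197 assessable per arm. Then 196.1 / 0.77 = 254.7, which reproduces the stated 255. The point does not depend on this figure; it supplies the assessable number used below.

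**3. Size of the effect, by assumption.** The SAP gives no rate of extension for poor response. Let x be the share of the experimental arm so extended and scored favourable, with none in control. The patients stay in the denominator. The unadjusted 95% upper bound is

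U = (pE − pC) + 1.96 × √[pC(1 − pC)/n + pE(1 − pE)/n].

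With n = 197, pC = 0.16 and pE = 0.21 when extensions count as unfavourable:

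U = 0.05 + 1.96 × √[(0.1344 + 0.1659)/197] = 0.05 + 1.96 × 0.03904 = 12.65%.

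With x = 1 point (about 2 of 197 patients), pE = 0.20:

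U = 0.04 + 1.96 × √[(0.1344 + 0.1600)/197] = 0.04 + 1.96 × 0.03866 = 11.58%.

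| n per arm | Control | Difference with extensions counted | U, x = 0 | x = 1 point | x = 2 points | x = 3 points |
|---|---|---|---|---|---|---|
| 197 | 16% | 5 points | 12.65% | 11.58% | 10.50% | 9.42% |
| 230 | 16% | 5 points | 12.08% | 11.01% | 9.94% | 8.86% |
| 197 | 5% | 7 points | 12.46% | 11.32% | 10.18% | 9.02% |

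The second row is close to full recruitment (300 × 0.77 = 231). Each assumed point lowers the bound by about 1.1 points.

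**4. Dependence on the arm.** With n = 197 and the first row's rates, suppose that 1 point is scored favourable in both arms (pC = 0.15, pE = 0.20). Then U = 0.05 + 1.96 × √[(0.1275 + 0.1600)/197] = 12.49%, almost unchanged from 12.65%. If it occurs in control only (pC = 0.15, pE = 0.21), U = 0.06 + 1.96 × √[(0.1275 + 0.1659)/197] = 13.56%, so the error works against non-inferiority. The direction depends entirely on where these patients arise.

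**The case against.** The strongest reply is that other wording in the SAP already makes these patients failures.

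- **Clinical failure.** It is part of the primary endpoint, and section 3.1 says that it "is defined as a change from protocol-specified TB treatment or retreatment for TB during follow up as determined by the treating physician". Extension for poor response can be read as such a change. This reading is possible, but extension is not named, and section 2 sends the reader to section 6 for the detailed definition. If clinical failure does include extension, section 6.1.4 omits part of the endpoint and still needs amending.
- **Extension as re-treatment.** Therapy beyond the treatment period falls in follow-up. If it counts as re-treatment, a patient who converts only afterwards never gains culture negative status and is caught by section 6.1.4(1). The SAP does not say that it counts so, and a patient who converted before an extension on clinical or radiographic grounds would still escape.
- **Loose use of change.** Sections 8(7) and 9.3 speak of changed treatment without naming extension, even where MITT is concerned. This supports ambiguity rather than a settled favourable classification.
- **Major protocol deviation.** Section 4.3(4) could exclude the patient. That depends on how the deviation is graded, and it would drop the failure rather than count it.

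A second reply limits the harm, and it stands. MITT is equally primary and explicitly counts these patients as unfavourable. Section 7 also looks for consistent ITT and sensitivity results, and results near the margin are to be weighed by their components. ITT gives less reassurance here, because section 6.1.2 defines unfavourable only as not favourable and so returns to section 6.1.1.

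A reader might infer that a failing regimen could be declared non-inferior through this gap alone, or that the cases would gather in the 4-month arms. The document supports neither. MITT would still show these failures, and if both primary analyses must meet the margin the gap alone cannot produce the claim, although section 7 gives no rule for disagreement between them. The SAP has no data on extension by arm; concentration in the shorter arms is plausible in an open-label trial but is inference.

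**Conclusion.** The inconsistency is real and probably an oversight. Sections 4.3(2), 6.1.3(6) and 6.1.4(6) do not fit together, and on a literal reading a patient extended for poor response who is culture negative at 12 months is unfavourable in MITT and favourable in PP. The section 3.1 wording on clinical failure leaves room for another reading, so what is established is a contradiction to be resolved, not a certain misclassification.

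Among the primary analyses the effect is confined to PP and to its agreement with MITT. Its frequency and its distribution over the arms cannot be known from the SAP. The 1.1-point shift in the bound per assumed point holds if the cases fall in an experimental arm and not in control. It uses an unadjusted interval, whereas section 7 specifies stratification by HIV status and cavitation. A change of verdict occurs only near the margin. Appendix 1 calls observed differences of 6 points or more highly unlikely, so the rows with a 16% control rate and a 5-point difference are the relevant ones and the 5% control row is a side case.

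**What to change.** Before database lock, add extension of treatment beyond that permitted by the protocol to the events in section 6.1.4(6), under the qualifier already there: only when it happens because of an unfavourable outcome, with or without bacteriological confirmation. Extensions for other reasons remain excluded under section 4.3(2). State in section 3.1 whether clinical failure includes such extension, so that the definition and the operative rule agree.

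The cost is one phrase in section 6.1.4 and one clarification in section 3.1. No patient is managed differently and no new data are called for beyond the reason for extension, which section 4.3(2) already needs. The PP unfavourable rate may become slightly higher. Settling it before lock avoids deciding individual classifications once results by arm are known.
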